### **11.2.2 Analysis of Secondary outcomes.**

#### **11.2.2.1 Change in the proportion of patients with COPD Assessment Test (CAT) $\geq 10$ (representing impaired health status) within three months after the switch**

Estimand:

- A. Population: Is defined through inclusion/exclusion criteria of the study protocol to reflect the target population.
- B. Variable: Binary variable response. Response is defined as having CAT score  $\geq 10$ .
- C. Intercurrent Event (IE): Include death, drop-out due to any adverse event (AE) and treatment discontinuation. For patients experiencing an IE, the most extreme unfavourable value will be assigned (patient CAT score  $\geq 10$ ).
- D. Population Level Summary: Odds ratio of response within 3 Months.

This endpoint will be analysed with a logistic GEE model with CAT response as dependent variable. Visit, GOLD group, smoking habits, packyears, sex, age, and comorbidities appearing at a rate greater than 5% will be entered as covariates and unstructured covariance matrix will be used.

Summaries of the estimated OR will be provided with 95% confidence interval. Model information will be provided as footnote under the corresponding table.

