9.3.3.2 Secondary outcomes

[figure not shown]
The secondary outcomes of the NIS include:

- Change in the proportion of patients with COPD Assessment Test (CAT) ≥ 10 (representing impaired health status) within three months after the switch
- Mean
- change from baseline in the total EQ VAS within three- months after the switch
- Proportion of patients that change (improve/worsen) each of the 5 dimensions of the

EQ-5D-5L within three-months after the switch

- Rate of adherence to medication of COPD patients according to the SMAQ three-months after the switch
- Mean total score in abbreviated PASAPQ (first 13 questions of Part 1) (patient satisfaction with the inhaler device) approximately three-months after the switch.
- Mean score of overall satisfaction according to Question 14 of PASAPQ (Part 1) three-months after the switch.
- Proportion of preference (Spiriva® Handihaler® vs Spiolto® Respimat®) according to PASAPQ (Part 2) three-months after the switch
- Mean score of willingness to continue with inhaler (Spiolto® Respimat®) according to PASAPQ (Part 2) three-months after the switch.

Mean change of patients' dyspnea status according to the mMRC scale within three-months after the switch.

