9.7.1 Main analysis

[figure not shown]
For the primary outcome, mean and 95% confidence interval will be presented.

Secondary outcomes will be evaluated by descriptive statistics:

All categorical variables will be summarized as relative and absolute frequencies. Proportions and 95% CI will be presented when appropriate.

The continuous variables will be reported by sample statistics: n (number of observations), number of missing data, mean, standard deviation (SD), minimum, first quartile (Q1), median, third quartile (Q3), and maximum.

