**TABLE 7.1.1 SHIFT CHANGES OF IMPAIRED HEALTH PATIENTS BASED ON OBSERVED DATA**

CAT Score	Baseline		3 Months						Total	
	>10		<10		Missing		n	%		
	n	%	n	%	n	%				
>10										
<10										
Missing										
Total										

**TABLE 7.1.2 SHIFT CHANGES OF IMPAIRED HEALTH PATIENTS BASED ON****TABLE 7.1.3 SHIFT CHANGES OF IMPAIRED HEALTH PATIENTS BASED ON**

Same shells as Table 7.1.1

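### The first secondary outcome is the change in the proportion with CAT ≥ 10, but the SAP's planned estimate with an interval is a covariate-adjusted odds ratio; no visible output plans the change in proportion with its 95% CI

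*SAP*

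**What the plan says.** Protocol 9.3.3.2 lists as its first secondary outcome: "Change in the proportion of patients with COPD Assessment Test (CAT) ≥ 10 (representing impaired health status) within three months after the switch". SAP 8.2.2 and the heading of SAP 11.2.2.1 repeat it. Protocol 9.7.1 has the secondary outcomes evaluated descriptively and adds: "Proportions and 95% CI will be presented when appropriate". SAP 11.2 carries an almost identical general sentence.

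Under the 11.2.2.1 heading, item D of the estimand is "Population Level Summary: Odds ratio of response within 3 Months". The analysis is then set out as follows:
- The model is a logistic GEE fitted to the CAT ≥ 10 indicator, with an unstructured covariance.
- Its terms are given in one sentence: "Visit, GOLD group, smoking habits, packyears, sex, age, and comorbidities appearing at a rate greater than 5% will be entered as covariates".
- The promised result is: "Summaries of the estimated OR will be provided with 95% confidence interval".

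Two groups of table shells in SAP Annex 1 serve this endpoint:
- Table 7.2.1 is titled as a change from baseline, but its columns are the odds ratio and its 95% CI.
- "TABLE 7.1.1 SHIFT CHANGES OF IMPAIRED HEALTH PATIENTS BASED ON OBSERVED DATA" is a baseline-by-Month-3 cross-tabulation with counts and percentages; Tables 7.1.2 and 7.1.3 use the same shell.

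**The concern.** The estimand's summary measure is not the quantity named in the outcome. For total CAT score, EQ-VAS and mMRC (SAP 11.2.1.1, 11.2.2.2 and 11.2.2.9), item D is the change itself, reported with a 95% CI. Here the outcome is also a change, yet the only model-based estimate with an interval is an odds ratio.

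The visible part of SAP 5.1 says that covariates were added to the model for this endpoint. It does not mention replacing a change in proportion by an odds ratio.

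The study tests no hypotheses (Protocol 9.5), so the estimate and its interval are the result. Patients whose physician has just stepped up treatment may well mostly have CAT ≥ 10. For a common outcome, an odds ratio read as if it were a ratio of proportions suggests a much larger change than occurred. Because the odds ratio is also conditional on covariates, it depends on how strongly they predict CAT ≥ 10, even when the proportions at the two visits are fixed. GOLD group is one of those covariates and is itself derived partly from the CAT score (footnote to Protocol Table 1), so their predictive strength may not be small.

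**Working it through.** **The plan's own figures.** The documents give no rate, effect size or precision target for CAT ≥ 10. The only planned size, 1310 evaluable patients, is for the mean CAT change. It reproduces: the probability of a half-width of at most 0.5 is 0.9007 at n = 1310 and 0.8971 at n = 1309. The point here does not depend on it. All rates below are assumptions.

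**Step 1: one change, two scales.** Assume 85% at baseline and 78% at Month 3.
- Difference: 78 - 85 = -7 points; relative change -7/85 = -8%.
- Marginal OR = (0.78/0.22) / (0.85/0.15) = 3.545 / 5.667 = 0.626.

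**Step 2: one odds ratio, many changes.** Month 3 proportion = OR × odds / (1 + OR × odds), where odds are the baseline odds.

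| Assumed baseline | Change at OR 0.626 | Change at OR 0.5 |
|---|---|---|
| 50% | -11.5 points | -16.7 points |
| 70% | -10.7 points | -16.2 points |
| 90% | -5.1 points | -8.2 points |
| 95% | -2.8 points | -4.5 points |

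The odds ratio alone therefore does not fix the change.

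**Step 3: effect of covariate adjustment.** A GEE odds ratio averages over patients who share the same covariate values, but it is still conditional on the covariates in the model. Let the covariate part of the linear predictor be normal with mean 0 and standard deviation s. Solve for the intercepts a0 and a1 that make the average of expit(a + s × Z) equal 0.85 and 0.78; the conditional OR is exp(a1 - a0).

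| s (assumed) | Conditional OR, with 85% and 78% fixed |
|---|---|
| 0 | 0.63 |
| 0.5 | 0.61 |
| 1 | 0.58 |
| 1.5 | 0.54 |
| 2 | 0.49 |

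The change is -7 points in every row.

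**Step 4: can the stated quantity be estimated well?** For paired data, SE = sqrt((b + c - (b - c)²) / n), where b and c are the proportions improving and worsening across the cutoff. Take b - c = 0.07 and n = 1500 × 0.85 = 1275.
- b + c = 0.13: half-width = 1.96 × sqrt((0.13 - 0.0049)/1275) = 1.9 points.
- b + c = 0.23: half-width = 1.96 × sqrt((0.23 - 0.0049)/1275) = 2.6 points.

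Under item C of the estimand, patients who die, drop out because of an adverse event or discontinue treatment are kept and counted as CAT ≥ 10. The number analysed would then lie between 1275 and 1500. At n = 1500 the same discordance gives half-widths of 1.8 and 2.4 points.

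**Step 5: do other outputs supply the estimate?**
- *Shift tables 7.1.1 to 7.1.3.* Both visit percentages and the discordant counts can be read off, so a raw change follows by hand. There is no difference column and no interval. Row and column labels are >10 and <10, so a score of exactly 10, which the outcome counts as impaired, has no cell.
- *The general sentence on proportions with 95% CI.* It is conditional and names neither this endpoint nor a change. At most it yields an interval for each visit's proportion, and two single-visit intervals do not give an interval for a paired difference.

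**The case against.** A reader might infer that the change cannot be obtained at all, or that an interval is possible only for the odds ratio. The documents do not support that. The shift tables are paired, so once the cutoff labels are put right a reader could compute both the change and, from the discordant counts, an interval. The general sentence in Protocol 9.7.1 and SAP 11.2 could also lead to an interval for each visit's proportion.

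A second tempting reading is that the odds ratio is an invalid analysis. It is not: a visit effect from a logistic GEE is a standard measure of change in a repeated binary outcome, and neither document says that the change must be an absolute difference. No decision threshold depends on the scale.

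Nor is exaggeration built in. In the same example the unimpaired share rises from 15% to 22%, a relative increase of 47%, and the odds ratio in that direction is 1.60. The odds ratio misleads only if it is read as a ratio of impaired proportions.

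Redaction also limits any claim of absence: part of SAP 5.1, the data basis of several 7.x tables, and SAP 11.3 cannot be seen.

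All of this narrows the point. What stands is that item D and Table 7.2.1 do not match the outcome they sit under, and no visible output plans the change in proportion with an interval.

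**Conclusion.** The mismatch holds, and it concerns the choice of summary measure and its reporting. The modelled variable (CAT ≥ 10 by visit) is the right one; the planned estimate is on a scale that does not answer the stated objective. Under the assumed fall from 85% to 78%, the outcome is a change of -7 points, while the reported odds ratio could lie anywhere from about 0.61 to 0.49 for a covariate SD of 0.5 to 2. At the weaker end of that range the shift from the marginal 0.63 is modest.

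The sizes rest wholly on assumed rates, covariate strength and discordance, since the documents give none of these. The mismatch itself rests only on the visible text. It should be corrected, but it affects a secondary outcome whose raw change is partly recoverable from the planned tables.

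**What to change.** 1. In SAP 11.2.2.1, change item D to the difference in the proportion with CAT ≥ 10, Month 3 minus baseline, with 95% CI.
2. Name one estimator: average the predicted probabilities at each visit from the GEE already planned, over the same patients and with the covariates held at their baseline values, under the intercurrent-event rule already stated. Use a robust, delta-method standard error.
3. In Table 7.2.1, show both proportions and the difference with its 95% CI. Keep the odds ratio as supplementary and label it as conditional on the listed covariates.
4. Give the observed-pair difference as descriptive support. It uses only complete pairs, so it can differ from the model-based figure and should not be an interchangeable alternative.
5. Relabel shells 7.1.1 to 7.1.3 as ≥10 and <10.

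The cost is SAP wording, one post-estimation step and edited shells, with no new data. The one drawback is that the headline figure may look less striking than the odds ratio.

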#### **11.2.2.2 Mean change from baseline in the total EQ VAS within three- months after the switch**

Estimand:

- A. Population: Is defined through inclusion/exclusion criteria of the study protocol to reflect the target population.
- B. Variable: Continuous variable response.

C. Intercurrent Event (IE): Include death, drop-out due to any adverse event (AE) and treatment discontinuation. For patients experiencing an IE, the most extreme unfavourable value will be assigned (EQ-VAS equals to 0).

D. Population level summary: The change from Baseline of EQ-VAS score within 3 Months.

This endpoint will be analysed with a Mixed Model for Repeated Measures (MMRM) with EQ-VAS score as dependent variable. Visit, GOLD group, smoking habits, packyears, sex, age, and comorbidities appearing at a rate greater than 5% will be entered as covariates. Patients will be fitted at random and an unstructured covariance matrix will be used, allowing adjustment for correlations between study visits within the study patients. The Kenward- Roger degrees of freedom approximation will be used in the model (ddfm=kr).

Summaries of the estimated mean change from baseline of EQ-VAS score at 3 Months will be provided with 95% confidence interval. Model information will be provided as footnote under the corresponding table

#### 11.2.2.3 Proportion of patients that change (improve/worsen) each of the 5 dimensions of the EQ-5D-5L within three-months after the switch

Estimand:

A. Population: Is defined through inclusion/exclusion criteria of the study protocol to reflect the target population.

B. Variable: Ordinal variable response.

C. Intercurrent Event (IE): Include death, drop-out due to any adverse event (AE) and treatment discontinuation. For patients experiencing an IE, the most extreme unfavourable value will be assigned

D. Population level summary: Odds ratio of improvement.

This endpoint will be analysed with an ordinal logistic GEE model with EQ-5D-5L response as dependent variable. Visit, GOLD group, smoking habits, packyears, sex, age, and comorbidities appearing at a rate greater than 5% will be entered as covariates and an unstructured covariance matrix will be used. This model will be repeated for each of the 5 dimensions.

Summaries of the estimated OR will be provided with 95% confidence interval. Model information will be provided as footnote under the corresponding table.

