Data analysis:	
Primary outcome
 
Mean change in patient's quality of life (QoL) according to the total CAT score within three-months after the switch from Spiriva® Handihaler® to Spiolto® Respimat® according to the daily clinical practice.
 
Secondary outcomes:
 
1. Change in the proportion of patients with CAT ≥ 10 (representing impaired health status) within three months after the switch2. Mean change from baseline in the total EQ VAS within three-months after the switch3. Proportion of patients that change (improve/worsen) each of the 5 dimensions of the EQ-5D-5L within three-months after the switch4. Rate of adherence to medication of COPD patients according to the Simplified Medication Adherence Questionnaire (SMAQ) three-months after the switch5. Mean total score in abbreviated Patient Satisfaction Questionnaire (PASAPQ; first 13 questions of Part 1) (patients' satisfaction with inhaler devices) three-months after the switch6. Mean score of overall satisfaction according to Question 14 of PASAPQ (Part 1) three-months after the switch7. Proportion of preference (Spiriva® Handihaler® vs Spiolto® Respimat®) according to PASAPQ (Part 2) three-months after the switch.8. Mean score of willingness to continue with inhaler (Spiolto® Respimat®) according to PASAPQ (Part 2) three-months after the switch9. Mean change of patients' dyspnea status according to the modified Medical Research Council (mMRC) scale within three- months after the switch		

Name of company: Boehringer Ingelheim			
Name of finished medicinal product: Spiolto® Respimat®			
Name of active ingredient: R03AL06 Tiotropium bromide plus olodaterol			
Protocol date: 04 June 2020	Study number: 1237-0098	Version/Revision: Final Version 4.0	Version/Revision date: 09 Jul 2021
Title of study:	Quality of life and preference of COPD patients after switching from Tiotropium monotherapy (Spiriva® Handihaler®) to dual therapy with Tiotropium bromide plus Olodaterol (Spiolto® Respimat®) under real life conditions in Greece (ELLACTO II study)		

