### **8.2.2 Secondary outcomes**

The secondary outcomes of the current study include:

- Change in the proportion of patients with COPD Assessment Test (CAT)  $\geq 10$  (representing impaired health status) within three months after the switch

- Mean change from baseline in the total EQ VAS within three- months after the switch
- Proportion of patients that change (improve/worsen) each of the 5 dimensions of the EQ-5D-5L within three-months after the switch
- Rate of adherence to medication of COPD patients according to the SMAQ three-months after the switch.
- Mean total score in abbreviated PASAPQ (first 13 questions of Part 1) (patient satisfaction with the inhaler device) approximately three-months after the switch.
- Mean score of overall satisfaction according to Question 14 of PASAPQ (Part 1) three-months after the switch.
- Proportion of preference (Spiriva® Handihaler® vs Spiolto® Respimat®) according to PASAPQ (Part 2) three-months after the switch
- Mean score of willingness to continue with inhaler (Spiolto® Respimat®) according to PASAPQ (Part 2) three-months after the switch.
- Mean change of patients' dyspnea status according to the mMRC scale within three-months after the switch.

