**TABLE 9.6.1.1 CHANGE FROM BASELINE ON THE MOBILITY DIMENSION DURING THE TRIAL BASED ON [REDACTED]**

Visit	OR of improvement	95%CI for OR
Month 3		
Covariate 1...n		

Footnote: adjusted for covariates OR: Odds Ratio

**TABLE 9.6.1.2 CHANGE FROM BASELINE ON THE MOBILITY DIMENSION  
DURING THE TRIAL BASED ON [REDACTED]**

**TABLE 9.6.2.1 CHANGE FROM BASELINE ON THE SELF-CARE DIMENSION  
DURING THE TRIAL BASED ON [REDACTED]**

**TABLE 9.6.2.2 CHANGE FROM BASELINE ON THE SELF-CARE DIMENSION  
DURING THE TRIAL BASED ON [REDACTED]**

**TABLE 9.6.3.1 CHANGE FROM BASELINE ON THE USUAL ACTIVITIES  
DIMENSION DURING THE TRIAL BASED ON [REDACTED]**

**TABLE 9.6.3.2 CHANGE FROM BASELINE ON THE USUAL ACTIVITIES  
DIMENSION DURING THE TRIAL BASED ON [REDACTED]**

**TABLE 9.6.4.1 CHANGE FROM BASELINE ON THE PAIN/DISCOMFORT  
DIMENSION DURING THE TRIAL BASED ON [REDACTED]**

**TABLE 9.6.4.2 CHANGE FROM BASELINE ON THE PAIN/DISCOMFORT  
DIMENSION DURING THE TRIAL BASED ON [REDACTED]**

**TABLE 9.6.5.1 CHANGE FROM BASELINE ON THE ANXIETY/DEPRESSION  
DIMENSION DURING THE TRIAL BASED ON [REDACTED]**

**TABLE 9.6.5.2 CHANGE FROM BASELINE ON THE ANXIETY/DEPRESSION  
DIMENSION DURING THE TRIAL BASED ON [REDACTED]**

Same shells as 9.6.1.1

**TABLE 10.1.1 SUMMARIES OF SMAQ QUESTIONNAIRE BASED ON OBSERVED  
DATA.**

N=xxx

Forget to take the medication for IPF

Yes

No

Missing

Always take your medication for IPF at the indicated time.

Yes

No

Missing

If feel worse, do you stop taking the medication for IPF?

Yes

No

Missing

At the last week, How often did you miss the medication for IPF?

Never

1-2 times

3-5 times

6-10 times

More than 10 times

At the past 3 Months

N=xxx

Days of missed medication for IPF

n  
 Mean  
 Median  
 SD  
 Minimum  
 Maximum  
 Q1  
 Q3  
 Missing

Days of missed one of the two daily doses of medication for IPF

n  
 Mean  
 Median  
 SD  
 Minimum  
 Maximum  
 Q1  
 Q3  
 Missing

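### SAP 11.2.2.3 names the proportions improving and worsening on each EQ-5D-5L dimension, but summarises them by a marginal odds ratio that determines neither

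*SAP*

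**What the plan says.** The Protocol abstract lists as a secondary outcome the "Proportion of patients that change (improve/worsen) each of the 5 dimensions of the EQ-5D-5L", and Protocol 9.3.3.2 repeats it. SAP 8.2.2 keeps it: "Proportion of patients that change (improve/worsen) each of the 5 dimensions of the EQ-5D-5L within three-months after the switch". Protocol 9.7.1 plans descriptive statistics for secondary outcomes.

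SAP 11.2.2.3 carries the same outcome name in its heading. Its estimand then reads "Variable: Ordinal variable response" and "Population level summary: Odds ratio of improvement". The analysis is "an ordinal logistic GEE model with EQ-5D-5L response as dependent variable". On the regressors it says: "Visit, GOLD group, smoking habits, packyears, sex, age, and comorbidities appearing at a rate greater than 5% will be entered as covariates". An unstructured covariance is used and the model is repeated for each dimension. After an intercurrent event the worst value is assigned.

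Two sets of output belong to this outcome in SAP Annex 1:

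- **Shift tables 9.1.1 to 9.5.3** cross baseline level with Month 3 level. Only the mobility shell (Table 9.1.1) is printed; it has three levels and the other tables reuse it. SAP section 8 and the questionnaire in Protocol Annex 3 have five levels, although the description in Protocol 9.3.1 says three.
- **Model tables 9.6.1.1 to 9.6.5.2** give one Month 3 odds ratio with a 95% CI, in a column headed "OR of improvement".

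**The concern.** The named outcome is a statement about individual patients: what share moved to a better level and what share moved to a worse one. It needs each patient's two levels taken together. The population-level summary is instead a comparison of two distributions, in which improvers and worseners offset each other. The label invites the reader to take the number as the odds that a patient improved.

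What is at stake is interpretation. One value of the odds ratio fits a cohort in which a quarter improve and almost nobody worsens. It also fits a cohort in which four in ten improve and more than two in ten worsen. Those are different findings about a switch of treatment, and the table designated for this estimand cannot tell them apart.

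**Working it through.** The documents give no expected figure or EQ-5D-5L distribution for this outcome, so there is no planned number to reproduce. The check is what the model can and cannot identify.

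**1. The two quantities.** Let π(j,k) be the probability of level j at baseline and level k at Month 3, with 1 the best level and 5 the worst.

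- Improved = sum of π(j,k) over k < j. Worsened = sum of π(j,k) over k > j. Both need the joint table.
- The model, with t = 0 at baseline and 1 at Month 3, is logit P(level at t ≤ c) = α(c) + β·t + covariates. So exp(β) is the odds of being at level c or better at Month 3 relative to baseline. It depends on the row and column totals of the joint table. The within-patient association affects the standard error, not what β measures.

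**2. Could the response be the change itself?** No. With a change category as response there is one row per patient, so a visit covariate and a within-patient covariance would have no meaning. SAP 11.2.2.3 lists visit among the covariates and defines no improved/unchanged/worsened variable.

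**3. Illustration with no net shift.** Assume the same level shares at both visits, so the odds ratio is exactly 1, and link the visits through a bivariate normal with correlation r. By symmetry, improved = worsened = (1 − P(same level)) / 2.

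| Assumed shares, levels 1 to 5 | r = 0.3 | r = 0.6 | r = 0.9 |
|---|---|---|---|
| 30/30/25/12/3% | 34% each | 29% each | 18% each |
| 80/15/4/0.7/0.3% | 15% each | 12% each | 7% each |

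**4. Illustration with a shift.** Assume 20/30/30/15/5% at baseline and 30/32/24/10/4% at Month 3. The cumulative odds ratios for a better level at the four cut-points are:

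- (0.30/0.70)/(0.20/0.80) = 1.71
- (0.62/0.38)/(0.50/0.50) = 1.63
- (0.86/0.14)/(0.80/0.20) = 1.54
- (0.96/0.04)/(0.95/0.05) = 1.26

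Two joint tables with these margins were built from starting weights exp(−2.5·|j−k|) (strong association) and exp(−0.5·|j−k|) (weak association). An ordinal GEE on visit alone, with working independence, was fitted to about 1500 patients from each.

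| Within-patient association | Improved | Worsened | Visit odds ratio (95% CI) |
|---|---|---|---|
| Strong | 24.7% | 1.4% | 1.61 (1.52 to 1.69) |
| Weak | 39.0% | 22.3% | 1.60 (1.44 to 1.77) |

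The difference between 1.61 and 1.60 comes from rounding cell counts to whole patients.

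**5. Precision of the named outcome.** The largest 95% half-width of a proportion is 1.96·√(0.25/N). At N = 1500 this is 2.5 percentage points. At N = 1500 × 0.85 = 1275, using the Protocol's 15% dropout, it is 2.7 points.

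**The case against.** The strongest reply is that the plan contains more than the model. The shift tables cross each patient's two levels with n and %, so cells on one side of the diagonal add up to improved and those on the other to worsened. SAP 11.2 also promises summary statistics for all secondary endpoints, and proportions with 95% CIs where appropriate. This stands, and it rules out an inference a reader might draw, that the named outcome is not estimated at all. The transitions are planned. What is missing is a defined improved or worsened total, a CI tied to this outcome, and a link from the estimand to those tables. The SAP does name a proportion as the summary where it wants one, in 11.2.2.4 and 11.2.2.7.

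A second reply is that the public SAP lacks the text of section 11.3, and the data basis of many tables is blacked out. That also stands: the redacted text may say more. The mismatch within 11.2.2.3 does not depend on it, because outcome name, summary, model and label are all legible.

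Third, the three-level shell is a template slip that contradicts the SAP's own section 8. Agreed: it does not show that the proportions were unplanned. It matters here only because the fallback tables cannot hold the data as drawn.

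Fourth, a reader might infer that the odds ratio is worthless. The documents do not support that: a net shift in levels bears on the secondary objective of evaluating change in quality of life by EQ-5D-5L. This is also one of nine secondary outcomes in a single-cohort study that tests no hypothesis.

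**Conclusion.** The point holds as a mismatch between the named outcome and its population-level summary. The visit odds ratio is a marginal cumulative odds ratio, and it is mislabelled in Table 9.6.1.1 and in every table that reuses that shell. This follows from the model as written and needs no assumption about the data, beyond margins that allow more than one transition table.

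The sizes are illustrations under assumed level shares and associations. At an odds ratio of 1, improved and worsened are each 18% to 34% under one set of shares and 7% to 15% under another. Neither range bounds what this study will show. Confidence is high on the mismatch and the label. It is lower on whether any redacted text already specifies the proportions with CIs. The plan should be changed, but neither the primary outcome nor the data collection is affected.

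**What to change.** In SAP 11.2.2.3 and Annex 1:

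1. For each dimension, derive a patient-level category from Month 3 level against baseline level: improved, unchanged or worsened.
2. Make the population-level summary the improved and worsened proportions, each with a 95% CI, in one small table per dimension.
3. State that the existing worst-value rule for intercurrent events is applied before classification. State how a patient already at level 5 at baseline is then counted, since assigning level 5 at Month 3 would otherwise make that patient unchanged. Show the observed-data version beside it.
4. Correct the shift-table shells to five levels with each dimension's own wording, and refer to them from the estimand.
5. Keep the GEE as a supportive analysis, relabelled *marginal cumulative odds ratio of a better level, Month 3 vs baseline*.

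Improved minus worsened with a paired CI is a reasonable optional addition; it is not a named outcome. The cost is one derived variable and one small table per dimension, with no new data.
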